5.3.8 Adverse event collection and reporting

AE Collection:

The following must be collected and documented on the appropriate eCRF by the Investigator:

• From signing the informed consent onwards through the Residual Effect period (REP), until the end of the REP (for this trial it will be classed as 28 days after the end of the PK evaluation period):

- all AEs (non-serious and serious) and all AESIs.

• After the individual patient's end of trial: the investigator does not need to actively monitor the patient for AEs but should only report relevant SAEs and relevant AESIs of which the investigator may become aware of.

Figure 5.3.8:1 Adverse Event Collection and Reporting

The REP is defined as 28 days after the last trial medication application (for this trial it will be classed as 28 days after the end of the PK evaluation period; this is a general diagram and there will be no run-in period in this trial. Treatment will be classed as the PK evaluation period). All AEs which occurred through the treatment phase and throughout the REP will be considered as

on treatment please see section 7.3.4. Events which occurred after the REP will be considered as post treatment events.

AE reporting to sponsor and timelines:

The Investigator must report SAEs, AESIs, and non-serious AEs which are relevant for the reported SAE or AESI, on the BI SAE form via fax immediately (within 24 hours) to the Sponsor's unique entry point (country specific contact details will be provided in the ISF). The same timeline applies if follow-up information becomes available. In specific occasions the Investigator could inform the Sponsor upfront via telephone. This does not replace the requirement to complete and fax the BI SAE form.

With receipt of any further information to these events, a follow-up SAE form has to be provided. For follow-up information the same rules and timeline apply as for initial information.

Information required:

For each AE, the Investigator should provide the information requested on the appropriate eCRF pages and the BI SAE form, e.g. onset, end date, intensity, treatment required, outcome, seriousness, and action taken with the investigational drugs. The Investigator should determine the causal relationship to the trial medication and any possible interactions between the investigational drugs.

The following should also be recorded as an (S)AE in the eCRF and SAE form (if applicable):

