6. INVESTIGATIONAL PLAN

6.1 **VISIT SCHEDULE**

Informed consent of all study patients will be obtained in compliance with ICH and GCP guidelines and the principles stipulated in the Declaration of Helsinki prior to any study related procedures, including washout of restricted medications.

The study will consist of three sequential periods; a screening period, a PK evaluation period, and the follow-up period.

Screening will be up to 4 weeks (28 days) in duration. The PK evaluation period will be 24 days in Group 1 and 16 days in Group 2 plus a follow up period of 28 days.

All patients are to adhere to the visit schedule as outlined in flowchart 1 and flowchart 2. Some flexibility is allowed in scheduling the visits according to the visit time windows specified. The trial medication dispensed allows for these time windows. All deviations from the planned schedule will be documented. If any visit is to be rescheduled, subsequent visits should follow the previous visit date schedule. No protocol waivers will be given (e.g. sponsor will not grant permission to include a known ineligible patient).

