- Remind patient not to take morning dose of study medication on the day of Visit 3 and to bring their study medication with them to the clinic and also the diary card.

Visit 3 Day 23

Once the patient has been on stable, full dose pirfenidone for 7 days (a 6 day window is allowed to ensure 7 consecutive days) they will return to clinic for the next PK day.

The patient should attend the clinic at approximately 07:00 so that the following assessments can be started before breakfast is given:

- Physical examination and vital signs.
- Urine pregnancy test for women of childbearing potential.
- Blood sample for laboratory tests (Section 5.3.3)
- Pre-dose PK samples should be taken according to PK Flowchart (Group 1, this should be taken prior to the other blood samples).
- •
- Spirometry.
- Review concomitant therapy and any adverse events since previous visit and throughout the day at regular intervals.
- Patients will return all unused medication. Medication compliance will be assessed by counting returned (unused) capsules.
- The patient will return the diary card and this will be reviewed to check that the patient has received seven consecutive, stable days of treatment.
- One 150mg nintedanib capsule and three 267 mg pirfenidone capsules should be given to the patient at should be given to the patient at 08:00 during breakfast (See PK Flowchart – Group 1).
- PK samples should be taken according to PK Flowchart (Group 1).
- The patient should be given lunch at 12:00.
- Three 267 mg pirfenidone capsules will be given to the patient at 14:00 along with a snack.
- A snack will also be given to the patient at 16:00.
- After the PK time point at 18:00, the patient can leave the clinic.
- The patient should take the final dose of three 267 mg pirfenidone capsules at home at approximately 20:00 with food and a glass of water.

Visit 3 Day 24

- The patient must return the next morning (Visit 3 Day 24) for the 24 hour PK time point at 07:55 the next day.
- AEs and concomitant medications should also be assessed.
- Other assessments listed for Visit 3 in the PK Flowchart are conducted at Day 23
- No study drugs are given.
- Remind patient of PK FU visit scheduled for 28 days after this visit.

PK Follow-up/ End of Trial

The patient should return to the clinic 28 days or more after Visit 3 Day 24 for their PK Followup/ End of Trial Visit as detailed in section 6.2.3.

Group 2

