7.3.3 Further endpoint analyses

7.3.4 Safety analyses

All treated patients will be included in the safety analysis.

All adverse events with an onset between start and end of the residual effect period (REP), a period of 28 days after the last dose of trial medication will be assigned to the treatment period for evaluation and displayed by group (group 1 and group 2).

AEs recorded prior to intake of trial medication will be assigned to 'screening', those between first intake until the last intake of trial medication plus 28 days will be assigned to the 'on-treatment' period. Events occurring after the on-treatment period will be summarized as 'follow-up' period and those after the end of trial visit will be assigned to 'post-study' period.

Safety analyses will be descriptive in nature and will be based on BI standards. No hypothesis testing is planned.

Frequency, severity, and causal relationship of adverse events will be tabulated by system organ class and preferred term after coding according to the current version of the Medical Dictionary for Regulatory Activities (MedDRA).

Laboratory data will be analysed both quantitatively, as well as qualitatively. The latter will be done via comparison of laboratory data to their reference ranges. Values outside the reference range as well as values defined as clinically relevant will be highlighted in the listings. Laboratory data will be described with regard to distribution parameters as well as with regard to frequency and percentage of patients with abnormal values or clinically relevant abnormal values.

Vital signs, physical examinations, or other safety-relevant data observed at screening, baseline, during the course of the trial and at the end-of-trial evaluation will be assessed with regard to possible changes compared to findings before start of treatment.

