6. GENERAL ANALYSIS DEFINITIONS

6.1 TREATMENTS

For treatment specifications, see Section 4 of CTP.

The following trial periods will be defined: screening, post-entry, treatment period, off-treatment, Residual Effect Period, follow-up and post-study as follows:

Note: the last day of each of the following periods is excluded.

- **Screening:** from informed consent to date of entry
- **Post-entry** (if applicable): from entry to first trial drug intake.
- **Treatment period:** from first trial drug intake (or re-start of treatment if interruption) to last trial drug intake (or the day before start date of interruption, if interruption) plus one day
- **Off-treatment** (if applicable): from start date of interruption to re-start of treatment
- **Residual Effect Period:** from the last trial drug intake plus one day to last trial drug intake plus 28 days plus one day.
- **Follow-up** (if applicable): from last trial drug intake plus 29 days up to the beginning of post-study period. This period is only created if last trial drug intake took place more than 28 days before trial completion (i.e. date of the follow-up visit or date where the patient discontinued prematurely the trial).
- **Post-study:** from the latest of last trial drug intake plus 29 days or date of trial completion plus 1 day to database lock

For safety analyses, data up to 28 days after last trial drug intake (inclusive) will be considered on-treatment.

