7.8.1 Adverse events

Unless otherwise specified, the analyses of adverse events will be descriptive in nature. All analyses of AEs will be based on the number of patients with AEs and NOT on the number of AEs.

Furthermore, for analysis of AE attributes such as duration, severity, etc. multiple AE occurrence data on the CRF, will be collapsed into AE episodes provided that all of the following applies:

- The same MedDRA lowest level term was reported for the occurrences
- The occurrences were time-overlapping or time-adjacent (time-adjacency of 2 occurrences is given if the second occurrence started on the same day or on the day after the end of the first occurrence)
- Treatment did not change between the onset of the occurrences OR treatment changed between the onset of the occurrences, but no deterioration was observed for the later occurrence

For further details on summarization of AE data, please refer to the guidelines "Handling of missing and incomplete AE dates" ([3](#)) and "Analysis and presentation of adverse event data from clinical trials" ([4](#)).

The analysis of adverse events will be based on the concept of treatment emergent adverse events. That means that all adverse events occurring between first drug intake till 28 days after last drug intake (inclusive) will be assigned to the treatment. All adverse events occurring before first drug intake will be assigned to 'screening' and all adverse events occurring after last drug intake + 28 days will be assigned to 'post-treatment', 'follow-up' or 'post-study' (for listings only). Also, all AEs occurring between the start of an interruption and the end of interruption will be assigned to 'off-treatment' period in the listings. For details on the treatment definition, see [Section 6.1](#).

According to ICH E3 ([5](#)), AEs classified as 'other significant' will include those non-serious and non-significant adverse events with

- (i) 'action taken = discontinuation' or 'action taken = reduced', or

(ii) marked haematological and other lab abnormalities or lead to significant concomitant therapy as identified by the Clinical Monitor/Investigator at a Report Planning Meeting.

An overall summary of adverse events will be presented.

The frequency of patients with adverse events will be summarised by treatment group, primary system organ class and preferred term (mention MedDRA levels to be displayed in the tables). Separate tables will be provided for

- patients with serious adverse events

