7.8.5 Others

Not applicable, relevant physical examinations and spirometry findings are recorded as baseline condition or AEs.

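### An adverse event with onset at an on-schedule Group 1 Visit 4 (Day 52) reaches listings only, because the SAP's on-treatment period ends on Day 51

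*SAP*

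**What the plan says.** **Cut-off.** SAP 6.1 states: "For safety analyses, data up to 28 days after last trial drug intake (inclusive) will be considered on-treatment". Its follow-up period runs "from last trial drug intake plus 29 days up to the beginning of post-study period". Protocol 7.3.4 also ends on-treatment at last intake plus 28 days.

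**What happens to later events.** Protocol 7.3.4: "Events occurring after the on-treatment period will be summarized as 'follow-up' period". SAP 7.8.1: "all adverse events occurring after last drug intake + 28 days will be assigned to 'post-treatment', 'follow-up' or 'post-study' (for listings only"). SAP section 4 declares that all its analyses accord with the protocol.

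**The residual effect period in protocol 5.3.8.** The general definition there is 28 days after the last medication. The same section then adds: "for this trial it will be classed as 28 days after the end of the PK evaluation period". It counts events in that period as on treatment and refers the reader to 7.3.4. Protocol 6.1 gives the length: "The PK evaluation period will be 24 days in Group 1 and 16 days in Group 2".

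**Timing of Visit 4.** The Group 1 flow chart plans it for Day 52 with a +3-day window. Protocol 6.2.2 says: "The patient should return to the clinic 28 days or more after Visit 3 Day 24". The Group 2 flow chart plans it for Day 44, also +3 days.

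**How findings are analysed.** SAP 7.8.4 gives ECG no table, because relevant findings become baseline conditions or adverse events. SAP 7.8.5 does the same: "Not applicable, relevant physical examinations and spirometry findings are recorded as baseline condition or AEs". SAP 5.4.4 bases the maximum liver elevations on the worst on-treatment value.

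**The concern.** Visit 4 closes each patient's participation. In Group 1 it is planned one day after the SAP stops counting data as on-treatment; in Group 2 it is planned for the last day that counts. The SAP gives no reason for treating the groups differently. The difference arises because the Group 1 visit is counted from Day 24, the last PK sampling day, while the cut-off is counted from Day 23, the last dose.

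Three kinds of Group 1 data are affected.

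- **ECG.** The Group 1 flow chart schedules an ECG at Visits 1 and 4 only. The sole scheduled post-baseline ECG therefore falls outside the on-treatment period, and its findings have no other table.
- **Examination and spirometry.** A new abnormality with onset at Visit 4 appears only as an adverse event, and so only in a listing.
- **Liver tests.** Day 23 is the only day on which Group 1 is scheduled to take both drugs. Protocol 6.2.2 lists the Visit 3 laboratory sample among the assessments started before breakfast and the 08:00 doses. Visit 4 is then the only scheduled laboratory sample after co-administration, and the worst-value table leaves it out. Protocol 2.1 and 2.3 name liver enzyme elevation as an overlapping effect of the two drugs.

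**Working it through.** **Inputs.** Group 1: last intake Day 23 (flow chart footnotes 4 and 11); PK evaluation period ends Day 24 (protocol 6.1). Group 2: last intake and end of the PK evaluation period both Day 16. Visit 4 is planned for Day 52 and Day 44, each +3 days (flow charts).

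**Reproducing the planned visit days.** Group 1: 24 + 28 = 52. Group 2: 16 + 28 = 44. Both match. Counting Group 1 from the last dose would give 23 + 28 = 51, so the planned Day 52 is anchored on Day 24.

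**Comparing the cut-offs with the visit window.**

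| | Group 1 | Group 2 |
|---|---|---|
| SAP 6.1 and protocol 7.3.4: last intake + 28 | 23 + 28 = Day 51 | 16 + 28 = Day 44 |
| SAP follow-up period starts: last intake + 29 | Day 52 | Day 45 |
| Protocol 5.3.8, trial-specific: end of PK period + 28 | 24 + 28 = Day 52 | 16 + 28 = Day 44 |
| Visit 4 window | Days 52–55 | Days 44–47 |
| Window days on-treatment, SAP rule | 0 of 4 | 1 of 4 (Day 44) |
| Window days on-treatment, trial-specific 5.3.8 rule | 1 of 4 (Day 52) | 1 of 4 (Day 44) |

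**Does a late Visit 3 close the gap?** No. If Visit 3 slips by s days (0 to 6 are allowed), on-treatment ends on Day 51 + s, and 6.2.2 puts the earliest Visit 4 on Day 52 + s. At s = 6 these are Days 57 and 58.

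**Which Visit 4 data still reach a table?** SAP 6.7 allocates Group 1 vital signs from last intake + 28 to + 31, which is Days 51–54, to the Follow-up visit. Laboratory values from Day 39 onward, with no upper limit, go there too. A Day 52 visit falls inside both windows. SAP 7.8.3 tabulates vital signs by visit, and the laboratory summaries use the same allocated visits. One small gap remains: a permitted Day 55 visit lies one day past the vital-signs window (Table 6.7: 1), whereas the same formula fits the Group 2 window exactly (Days 44–47).

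**The case against.** The strongest reply is that the SAP follows the protocol's statistical section. SAP section 3 says it is based on protocol section 7, and 7.3.4 has the identical cut-off. This stands. A reader might infer that the SAP departs from the protocol on the cut-off, but that conflict lies inside the protocol, between the two anchors in 5.3.8 and the one in 7.3.4. The SAP itself departs from the protocol only in listing late events that 7.3.4 says will be summarised.

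A reader might also infer that nothing found at Group 1 Visit 4 reaches a safety table. The documents do not support that. Vital signs and laboratory values enter the by-visit tables. Events are assigned by when they occur, so a symptom reported at Visit 4 that began during the washout, up to Day 51, is tabulated. In SAP 5.4.4 only the maximum individual elevations are expressly limited to on-treatment values. Nor is Visit 4 the only safety contact after co-administration, since adverse events are also assessed on Day 24.

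Flow chart footnote 18 asks for at least 28 days after last intake, which taken alone would allow Day 51. That is correct, but the planned day, the window (+3 only) and 6.2.2 all make Day 52 the earliest scheduled day.

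Finally, one more day adds little to causal attribution. The longest half-life in protocol 1.2 is 19 h (nintedanib), so 28 days, or 672 h, is already about 672 / 19 = 35 half-lives. This stands as a reason to rate the point low. It does not explain why the same planned visit should be tabulated in one group and only listed in the other.

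**Conclusion.** The point holds for adverse events with onset at or after an on-schedule Group 1 Visit 4, and for the table of maximum liver elevations. None of the four scheduled Visit 4 days in Group 1 is on-treatment under the SAP; in Group 2 the planned day is. SAP 7.8.1 contradicts protocol 7.3.4 on summarising later events, so the no-change statement in SAP section 4 is inaccurate on that item. Protocol 5.3.8 needs a single anchor.

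This rests on three assumptions: the patient completes Group 1 on schedule; a finding first seen at Visit 4 is given that date as its onset; and the listings-only remark in SAP 7.8.1 covers all three labels in its sentence. If that remark covered only the last label, the SAP would still specify no table for follow-up events.

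A reader might conclude that following 5.3.8 carries on-treatment through the whole Visit 4 window. It does not: it reaches Day 52 in Group 1 and leaves Group 2 at Day 44. Extending on-treatment to the end of the window would be a new definition found in neither document.

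Severity is minor. The safety analysis is descriptive, the events are still collected and listed, about 16 patients are planned for Group 1, and no primary PK result changes.

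**What to change.** 1. In SAP 7.8.1, add a table of follow-up adverse events by group, as protocol 7.3.4 states. This also covers visits on Days 53–55 in Group 1 and Days 45–47 in Group 2, which neither anchor reaches.
2. Use one residual-effect anchor in protocol 5.3.8, protocol 7.3.4 and SAP 6.1 and 7.8.1. The trial-specific anchor in 5.3.8, end of the PK evaluation period plus 28 days, covers Day 52 and leaves Group 2 unchanged. When that is settled, bring the Group 1 Follow-up window in SAP Table 6.7: 1 into line with Days 52–55.
3. In SAP 5.4.4, include the Visit 4 sample in the maximum liver elevation table, or show it in a separate post-baseline column.

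The cost is a few lines of wording, one derived date and one extra table. The downside is that at most a few late events or values, far from dosing, are counted.

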6.2 IMPORTANT PROTOCOL VIOLATIONS

The following table defines the different categories of important PVs. The final column describes which PVs will be used to exclude patients from the PKS. If the data show other important PVs, this table will be supplemented accordingly by the time of the MQRM/RPM/DBLM.

Table 6.2: 1 Important protocol violations

Category/ Code	Description	Example/Comment	Excluded from
A	Entrance criteria not met		
A1	Inclusion criteria not met	Inclusion criteria 2 to 6 Automatic IPV	None
A2	Exclusion criteria met	Exclusion criteria 1 to 21 Automatic IPV and Medical review of MQRM listings	None
B	Informed consent		
B1	Informed consent not given or given too late	Inclusion criteria 1 Automatic IPV	None
B2	Informed consent not given for pharmacogenetics samples (unspecified part) but pharmacogenetics test done	According to pharmacogenetics database and CRF Automatic IPV	None
B3	Informed consent not given for [REDACTED] but [REDACTED] test done	According to [REDACTED] and CRF Automatic IPV	None
C	Trial medication and randomisation		
C1	Incorrect trial medication taken	Manual IPV (see monitoring manual) and Medical review of MQRM listings	None
C2	Drug not permanently discontinued despite criteria of Section 3.8.1 of CTP met	Medical review of MQRM listings	None
D	Concomitant medication		
D1	Patient received restricted concomitant therapies during treatment phase	Medical review of MQRM listings.	PKS
E	Missing data		
E4	Certain violations of procedures used to measure primary data	Medical review of MQRM listings, to be decided no later than RPM.	PKS
F	Incorrect timing		
F5	Certain violations of time schedule used to measure primary data ¹ .	Medical review of MQRM listings, to be decided no later than RPM.	PKS

¹ Time deviations will only be flagged as important PV, when leading to exclusion of the entire subject from an analysis set
 Source: BI reference document "Protocol Violation Handling Definitions" (001-MCS-50-413_RD-01) (1)

6.3 PATIENT SETS ANALYSED

- **Screened set**

This patient set includes all patients having signed informed consent and performed visit 1.

- **Treated set (TS)**
 This patient set includes all patients who were dispensed study medication and were documented to have taken at least one dose of investigational treatment.

- **Pharmacokinetic analysis set (PKS)**
 The PKS will be used as defined in section 7.3 of the CTP.

The following table shows which patient set will be used for which study period and which class of endpoints.

Table 6.3: 1 Patient sets analysed

Class of endpoint	Patient set		
	Screened set	TS	PKS
Primary endpoint			X
Secondary endpoints			X
Further endpoints			X
Safety analyses		X	
Demographic/baseline characteristics / extent of exposure	X	X	

Note that the number of patients with available data for an endpoint may differ.

6.4 SUBGROUPS

This section is not applicable.

6.5 POOLING OF CENTRES

This section is not applicable because centre/country is not included in the statistical model.

6.6 HANDLING OF MISSING DATA AND OUTLIERS

The endpoints will be used as defined in Section 7.5 of the CTP.

Data of treated subjects who failed to complete all stages of the study (subjects who withdraw consent or are removed from the trial) will be reported as far as data are available. It is not planned to impute missing values.

For previous/concomitant therapies, in case of (partially) missing start and end dates of concomitant therapies, the dates will be imputed so that the extent of exposure to the concomitant therapy is maximal, i.e. the first day (month) of the month (year) for incomplete start dates and the last day (month) of the month (year) for incomplete end dates.

Missing or incomplete AE dates will be imputed according to BI standards (see "Handling of missing and incomplete AE dates") (3).

Handling of missing PK data will be performed according to the BI standard procedure "Noncompartmental Pharmacokinetic / Pharmacodynamic Analyses of Clinical Studies" (001-MCS-36-472_RD-01) (2).

